6.8 Usual care group

Patients randomized to the usual care arm will undergo monitoring with laboratory measurements as outlined in the study protocol (6.13: Follow-up evaluations Weeks 1, 2 and 6.14: The assessment period Weeks 3, 4 and 6). The patients will continue to have standard of care (SOC) monitoring by the study team and by the dialysis care team. They will continue to have SOC teaching and follow-up with the renal dietitian in the clinic.

6.9 Therapies for all randomized patients throughout the study

For all study participants, the dialysis prescription will not be changed throughout study. ACE inhibitor and angiotensin receptor blocker medications will be unchanged throughout study. Calcitriol or active vitamin D analogues, nutritional vitamin D, calcimimetics, multivitamins, and prescribed phosphate binder medication will be managed by the rounding clinician throughout study and will not be altered by the study protocol.

All patients will be provided oral instructions at the start of the trial on adherence with low potassium diets. All patients will receive dietary instruction from the clinic dietitian, with the goal of limiting potassium intake to less than 60 mEq per day. This is the standard of care. The clinic dietitian will be blinded to the patient group assignment in the study. Subjects will be encouraged not to change their food and diet habits during the study period. The prescription of other oral potassium binders will be prohibited in the study. All study participants will also be given a printed flyer for instruction on a low potassium diet.

6.10 Seven day cardiac monitor

The long-term heart monitor (LTHM) to be used in this study is a dual –channel wearable cardiac monitor that is applied as a skin patch. The Medicomp Telepath records cardiac rhythms for up to 7 days (medicompinc.com; last accessed 5/1/19).

The first LTHM, Telepatch #1 will be applied at the end of HD3 prior to Week 0 and removed at the beginning of HD3 of Week 0. The second LTHM, Telepatch #2, will be applied at the end of HD3 at the end of HD3 and removed at the beginning of HD3 of Week 4.

When the cardiac monitor is applied to a patient, a user guide and a symptom diary will be provided.

6.11 Electrocardiography (ECG)

A 12 lead ECG will be performed during Week 0. The patient will go to an outpatient Duke cardiology clinic for the ECG.

6.12 Concomitant medications

Except for those listed in the exclusion criteria, all medications (prescription or over-the-counter) initiated prior to enrollment may be continued during the course of the study.

All medications that are continued from the start of the study or that are started during the study (other than the study medication) including prescription or over-the-counter will be documented by the study team.

6.13 Follow-up evaluations Weeks 1, 2

A member of the study team will see the patient at the start of HD1 Week 1. Weight, pulse and blood pressure will be recorded. A pre-dialysis serum potassium lab sample will be collected and sent to the clinical lab. Concomitant medications will be recorded.

With study team visit on HD2 or HD3 of Week 1, the patiromer dose will be titrated based on the pre-dialysis potassium measured at HD1. Patiromer will be increased by 8.4 g/day if $K \geq 5.5$ meq/L, decreased by 8.4 g/day if $K < 4.5$ mEq/L, and patiromer will be discontinued if $K < 4$ mEq/L.

6.14 The assessment period Weeks 3, 4 and 6

A member of the study team will see the patient at the start of HD1 Week 3 and HD1 Week 4. Weight, pulse and blood pressure will be recorded. A pre-dialysis serum potassium lab sample will be collected and sent to the clinical lab to measure potassium. Concomitant medications will be recorded.

With study team visit on HD1 of Week 3, the patiromer dose will be titrated based on the pre-dialysis potassium measured at HD1. Patiromer will be increased by 8.4 g/day if $K \geq 5.5$ meq/L, decreased by 8.4 g/day if $K < 4.5$ mEq/L, and patiromer will be discontinued if $K < 4$ mEq/L.

The long term heart monitor (LTHM; Telepatch #2) will be placed at the end of HD3 Week 3 and removed at the beginning of HD3 of Week 4.

With study team visit on HD1 of Week 6, weight, pulse and blood pressure will be recorded. A pre-dialysis blood sample will be collected and sent to the clinical lab for a renal function panel. Concomitant medications will be recorded.

6.15. Withdrawal of subjects.

A subject may discontinue participation in the study at any time without being obligated to give a reason, although they are free to do so if they wish.

If a subject does withdraw from the study, the Investigator must make every effort to perform all post-study assessments. Safety and tolerability data on the subject will be evaluated and reported. The Investigator may withdraw a subject due to non-compliance with the protocol requirements, or if an event occurs which would interfere with the objectives of the study.

Subjects must be withdrawn from the study if:

1. Informed consent is withdrawn voluntarily by the subject.
2. The Investigator believes it is in the best interest of the subject to be removed from the study.
3. The serum potassium levels exceeds 7 mEq/L during Week 2 to 7 and, the first sample is confirmed by a second sample exceeding 7 mEq/L at an unscheduled visit within one week.

4. A serious adverse event occurs (the Investigator must consider severity of the event and relatedness to study medication).

5. A significant protocol violation occurs.

The date and reason for discontinuation must be noted and a brief discontinuation summary must be filled out. Serious Adverse Events should be followed up until resolution or for 30 days after discontinuation. All efforts should be made to have subjects that discontinue from study return the remainder of their study medication.

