1. Not considered by the treating physician(s) to be adherent with recommended dialysis schedule and prescribed medications
2. Life expectancy < 3 months
3. Currently prescribed oral potassium supplements
4. Therapy with oral potassium-lowering medication in the prior three months,
5. Underlying severe gastrointestinal disorders, including history of ischemic bowel.
6. Corrected serum calcium concentration > 10.5 mg/dL in prior three months
7. Anticipated kidney transplant within the next 3 months
8. Prisoners or others who are involuntarily incarcerated or detained
9. Pregnant, breastfeeding, or considering pregnancy.
10. Participation in a clinical trial of an experimental treatment within the past 30 days

Duration of treatment:

Participants randomized to receive patiromer will receive the drug for a total of 4 weeks.

Withdrawal of subjects

Subjects will be withdrawn from the study and receive appropriate treatment for hyperkalemia (at the Investigator's discretion), if the serum potassium level exceeds 7 mEq/L during Week 2 to 7 and, the first sample is confirmed by a second sample exceeding 7 mEq/L at an unscheduled visit within one week.

Concomitant medications:

Subjects are not allowed to receive potassium binders during the study (e.g. sodium polystyrene sulfonate, or SPS) except in emergency situations.

Except for those listed in the exclusion criteria, all medications (prescription or over-the-counter) that have been started prior to screening may be continued during the course of the study.

Statistical analysis:

This is a proof-of-concept study, to determine the extent to which administration of patiromer has the potential to change the risk category for ESRD patients who are on conventional HD schedules. In addition, the study aims to develop and test study procedures and instruments that will be implemented in a large-scale clinical trial.

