8.1. Primary analysis

This is a proof-of-concept study, to determine the extent to which administration of patiromer has the potential to change the risk category for ESRD patients who are on conventional HD schedules. In addition, the study

aims to develop and test study procedures and instruments that will be implemented in a large-scale clinical trial.

By nature of the size of the study, the power of the trial will be limited for the primary analysis. The proposed primary endpoint is the between-group differences of the number of episodes, per subject, of serum K \geq 5.5 mEq/L during Weeks 3 and 4. This will be assessed as follows: Six serum samples will be collected and assessed for each patient during the efficacy phase (Weeks 3 and 4). Patients would receive a score of perfect K control (6 of 6 samples in range; Score 1.0), moderate K control (5 of 6 in range; Score 0.83), inconsistent K control (4 of 6 in range; Score 0.67), erratic K control (3 of 6 in range; Score 0.50), poor K control (2 of 6 in range; Score 0.33), very poor K control (1 of 6 in range; Score 0.17), or no K control (0 of 6 in range, Score 0). These scores will then be averaged for the patients in the active treatment group and the control group, and the results will be compared. Using this approach, a sample size of n=20 per group provides 86% power to detect a between-group difference of 2 in mean episodes of hyperkalemia per patient, assuming $\alpha=0.05$ and standard deviation 2.

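### Section 6.15 takes patients out of the study on grounds that can differ by arm, and does not secure their remaining Week 3–4 potassium draws

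*Combined protocol and SAP*

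**What the plan says.** Section 6.15 lists five grounds on which a subject has to leave the study. Items 1 and 2 are withdrawn consent and the investigator's view of the patient's best interest. The others are:

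- Item 3: "The serum potassium levels exceeds 7 mEq/L during Week 2 to 7", confirmed by a second value above 7 within a week. The synopsis repeats the rule: "Subjects will be withdrawn from the study and receive appropriate treatment for hyperkalemia".
- Item 4: "A serious adverse event occurs (the Investigator must consider severity of the event and relatedness to study medication".
- Item 5: "A significant protocol violation occurs".

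A discretionary ground stands before the list: "The Investigator may withdraw a subject due to non-compliance with the protocol requirements, or if an event occurs which would interfere with the objectives".

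For a subject who has left, "the Investigator must make every effort to perform all post-study assessments", and safety and tolerability data are reported. Post-study assessments are not defined, and the efficacy draws are not mentioned. The date and reason for discontinuation are recorded. Section 6.16 rules out replacement.

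Section 8.1 describes the primary endpoint: "Six serum samples will be collected and assessed for each patient during the efficacy phase (Weeks 3 and 4". Scores are listed for 6 of 6 down to 0 of 6 samples in range and are then "averaged for the patients in the active treatment group and the control group, and the results will be compared". There is no score for a patient with fewer than six samples, no defined analysis population and no dropout allowance.

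**The concern.** Leaving the study is a different matter from changing treatment. The protocol can separate the two: under sections 6.7, 6.13 and 6.14, potassium below 4 mEq/L stops patiromer without requiring study withdrawal. Section 6.15 makes no such separation.

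The grounds need not fall evenly on the arms. Confirmed potassium above 7 mEq/L is an extreme of the primary outcome (5.5 mEq/L or more) and is plausibly commoner without a binder. Item 4 weighs relatedness to a drug that only one arm takes. Dosing non-compliance can arise only on patiromer, and the decision to withdraw is made in an open-label trial.

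If the draws stop at withdrawal, the comparison of randomised groups becomes a comparison of those who stayed. Losing poorly adherent patiromer patients would enlarge the apparent effect. Losing usual-care patients with very high potassium would shrink it.

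**Working it through.** **Inputs from the documents.** 20 per group, SD 2 episodes, difference 2 episodes, α = 0.05, stated power 86% (section 8.1); 1:1 allocation (section 6.6). No withdrawal rate is given, so every count and every episode mean for withdrawn patients below is an assumption.

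**1. The plan's own figure.** Standardised difference 2/2 = 1. A two-sided two-sample t test with 20 per group has power 86.9%, which agrees with the stated 86%. The figure stands, and this point does not depend on it.

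**2. Which withdrawals matter.** The draws are pre-dialysis at the six sessions of Weeks 3 and 4.

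- Out before HD1 of Week 3: all six draws at risk. Under item 3 this needs a value above 7 in Week 2, confirmed before Week 3 begins.
- Out during Weeks 3–4: some draws already taken, the rest at risk.
- Out after the HD3 draw of Week 4: no effect on the primary endpoint.

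The figures below assume that all six draws are lost, so they are an upper case for each withdrawn patient.

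**3. Patiromer arm.** Let k of 20 be removed with mean m episodes, and let the rest average 1. Full mean = [(20 − k) × 1 + k × m]/20; after removal it is 1.

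- m = 3: k = 2 gives 1.2, k = 4 gives 1.4. The contrast is enlarged by 0.2 to 0.4.
- m = 2: 1.1 and 1.2. The contrast is enlarged by 0.1 to 0.2.

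**4. Usual care, item 3 only.** Let the full mean be 3, a total of 60 episodes. Remaining mean = (60 − k × m)/(20 − k).

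| k | m | Remaining mean | Shift |
|---|---|---|---|
| 1 | 5 | 55/19 = 2.89 | −0.11 |
| 2 | 5 | 50/18 = 2.78 | −0.22 |
| 1 | 6 | 54/19 = 2.84 | −0.16 |
| 2 | 6 | 48/18 = 2.67 | −0.33 |

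**5. Scale.** Standard error of the planned contrast = 2 × √(2/20) = 0.63. The largest shifts above are 0.4/0.632 = 0.63 and 0.333/0.632 = 0.53 standard errors. They can offset: two patiromer losses at m = 3 (+0.20) with one usual-care loss at m = 6 (−0.16) net to +0.04. A heavier assumption goes further. With m = 6, losing 3 or 4 usual-care patients gives 42/17 = 2.47 or 36/16 = 2.25, shifts of −0.53 and −0.75; the last exceeds one standard error.

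**6. Power.** Through numbers alone the cost is modest: 85.0% at 18 against 20, 82.5% at 16 against 20. Selective loss costs more. With true means of 3 and 1, SD held at 2 and lost controls at six episodes each, losing one leaves a difference of 1.84 and about 80% power; losing two leaves 1.67 and about 70%.

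**The case against.** The best defence is that these are ordinary withdrawal clauses in a 40-patient proof-of-concept study that admits limited power, and that few patients will meet them. Item 3 needs confirmation, and section 5.3 excludes non-adherent patients and those with potassium above 7 in the prior three months. This stands as a reason to expect small numbers. It is not complete protection: the synopsis list has a calcium criterion where section 5.3 has the potassium one, and entry requires recent hyperkalemia.

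A second defence is that the post-study assessments cover the gap. The phrase softens the point, but it is best effort and undefined, and reads more naturally as end-of-study checks than as six draws during the study. The section 2 flow chart is not visible in the text available and the schedule table is damaged, so an early-termination entry cannot be excluded.

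A third is that withdrawal above 7 mEq/L is a safety rule. Treating the patient is certainly right, but measuring potassium does not conflict with treating it.

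Three stronger readings are tempting and are not supported:

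- *Withdrawn patients are excluded from the analysis.* Section 8.1 does not say so; their handling is left open.
- *Non-compliance occurs only on patiromer.* The clause speaks of protocol requirements, which also bind usual care (blood draws, monitor wear, no other binders). Only dosing non-compliance is confined to one arm. Item 4 also asks for judgement, so not every serious adverse event removes a patient.
- *The rules favour patiromer.* The mechanisms pull in opposite directions, and nothing in the documents fixes the net sign.

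**Conclusion.** The point holds as a correctable weakness in design. Followed as written, section 6.15 ends study participation for outcome-related and potentially arm-related reasons without securing the data that section 8.1 needs. Only withdrawals before HD3 of Week 4 matter.

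The net direction is unknown. The size is probably small: below one standard error for every case with up to 4 patiromer or 2 usual-care patients lost, even with all six draws gone. That judgement rests on assumed counts and episode means; 4 usual-care losses at six episodes each would exceed one standard error. The main issue is selection, with a secondary cost in power if the loss is concentrated in high-potassium controls. Because the study also aims to develop procedures for a large-scale trial, the rule is worth correcting here.

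**What to change.** **Section 6.15 and synopsis.** State that a patient who meets item 3, 4 or 5, or the discretionary non-compliance or interfering-event ground, stays under observation. The remaining pre-dialysis Week 3–4 potassium draws and the Week 6 visit continue in both arms unless consent is withdrawn, the investigator judges this not to be in the patient's interest, or it is not feasible. Leave to the investigator whether patiromer is stopped, continued or adjusted. Confirmed potassium above 7 should not in itself require stopping a potassium binder.

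**Section 6.9.** Keep rescue treatment for potassium above 7 at the investigator's discretion, record it, and exempt it from the fixed dialysis prescription and the ban on other binders.

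**Section 8.1.** Analyse all randomised patients with any Week 3–4 draw in their assigned arm, scored as the proportion of available samples in range. Report by arm how many have fewer than six draws and how many have none. Add an on-treatment sensitivity analysis, and one that counts missing or post-rescue draws after confirmed potassium above 7 as episodes.

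**Cost.** Wording in four places. Patients already attend dialysis three times a week, so the draws need no new visits. Off-drug values will dilute the on-treatment effect, and post-rescue control values can shrink the contrast; the two sensitivity analyses show both. The proportion score weights one available sample like six, and patients with no draw still drop out of the main analysis, so selection is reduced rather than removed.

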6.16. Replacement of subjects

Subjects who are withdrawn will not be replaced.

7. Study medication

7.1 Description of medication

Patiromer is provided as a single-use packet containing a powder that can be suspended in water for oral administration. Patiromer is an off-white to light-brown powder; occasional white particles may be present. Each packet contains 8.4 g patiromer. Patiromer will be provided free of charge to study participants. Once the study is over, the remaining patiromer will be returned to Relypsa.

7.2 Treatment dispensing and administration

The coordinator will provide patiromer packets as outlined to the study participants who randomize to receive the study medication. The patient will be written instructions to take patiromer as follows:

- Measure ~1/3 cup of water. Pour half of the water into a glass, then add patiromer and stir. Add the remaining water and stir thoroughly. The powder will not dissolve completely and the mixture will look cloudy.
- Drink the mixture immediately. If powder remains in the glass after drinking, add more water, stir and drink immediately. Repeat as needed to ensure the entire dose is administered.
- Patiromer can be mixed with water, apple juice, or cranberry juice. Prepare each dose immediately prior to administration.
- Patiromer should not be heated (e.g., microwaved) or added to heated foods or liquids.
- Patiromer should not be taken in its dry form.

7.3. Storage requirements

Patiromer will be stored in the refrigerator at 2°C – 8°C (36°F – 46°F). If stored at room temperature (25°C ± 2°C [77°F ± 4°F]), patiromer must be used within 3 months of being taken out of the refrigerator. For either storage condition, do not use patiromer after the expiration date printed on the packet. Avoid exposure to excessive heat above 40°C (104°F).

8. Statistics

8.1. Primary analysis

This is a proof-of-concept study, to determine the extent to which administration of patiromer has the potential to change the risk category for ESRD patients who are on conventional HD schedules. In addition, the study

aims to develop and test study procedures and instruments that will be implemented in a large-scale clinical trial.

By nature of the size of the study, the power of the trial will be limited for the primary analysis. The proposed primary endpoint is the between-group differences of the number of episodes, per subject, of serum K \geq 5.5 mEq/L during Weeks 3 and 4. This will be assessed as follows: Six serum samples will be collected and assessed for each patient during the efficacy phase (Weeks 3 and 4). Patients would receive a score of perfect K control (6 of 6 samples in range; Score 1.0), moderate K control (5 of 6 in range; Score 0.83), inconsistent K control (4 of 6 in range; Score 0.67), erratic K control (3 of 6 in range; Score 0.50), poor K control (2 of 6 in range; Score 0.33), very poor K control (1 of 6 in range; Score 0.17), or no K control (0 of 6 in range, Score 0). These scores will then be averaged for the patients in the active treatment group and the control group, and the results will be compared. Using this approach, a sample size of n=20 per group provides 86% power to detect a between-group difference of 2 in mean episodes of hyperkalemia per patient, assuming $\alpha=0.05$ and standard deviation 2.

